To decrease the burden on patients, where local regulations allow, samples taken at home between visits or when a home visit occurs will be shipped by the patient or a nurse or equivalent function visiting the patient for analysis at a central laboratory. Where this is not possible alternative arrangements will be made, e.g. samples taken to the investigational site.

After end of treatment patients will continue with a 4-week follow-up with further urine and blood sampling. Beyond analysis for safety, urine and blood samples in this trial will serve for biomarker analysis including UACR and eGFR.

The trial will be stratified according to SGLT2 inhibitor use and type of diabetes at the time of randomisation. SGLT2 inhibitors are a promising class of drugs for DKD patients and it is anticipated that their use might increasingly become standard of care. [P20-09106]. To avoid a confounding effect, treatment with SGLT2 inhibitors will have to be kept stable prior to trial participation and throughout trial treatment (see [section 4.2.2.1](#)). An approximate of 10% patients on Type 1 Diabetes Mellitus patients will be expected.

All patients will start on 1 mg TID BI 685509 or matching placebo. If the medication is tolerated, up-titration to 2 mg TID BI 685509 or matching placebo will occur after 2 weeks for patients in dose groups 2 and 3, and up-titration to 3 mg TID BI 685509 or matching placebo will occur after another 2 weeks for patients in dose group 3. Patients will receive 20 weeks of treatment in total, which is expected to be the duration required to obtain stable effects.

Following the 20-week treatment period, or at the time trial treatment is permanently discontinued, patients will have an End of Treatment (EoT) visit, which will be the start of a 4-week follow-up period. A first follow-up telephone call (FUp1) at least 7 days later is considered as the end of the Residual Effect Period (REP). Until the end of REP all AEs and changes to concomitant medication need to be collected, documented and reported.

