In this parallel design, double-blind conditions regarding the patient's treatment (active or placebo) are maintained within each dose group. It is not feasible to apply double-blind conditions between dose groups because the individual tablet strengths and matching placebo look different. Therefore investigators will know which dose group their patient is in but will be blinded to whether they are on active drug or placebo. Patients will be blinded to both the dose group they are on and whether they are taking active drug or placebo. Keeping investigators blinded to the dose group would require patients to take multiple tablets three times a day on top of the extensive background medication they already receive, which is considered too burdensome for this clinical trial. However, in order to minimise possible observer bias with regard to dose dependent effects, the dose group will be blinded to the patient as much as possible by applying the following measures:

The trial medication label will not include dose strengths so the dose will not be identifiable to the patient from the label.

Every effort should be made by the trial team and sites staff that the patient is not informed about the dose group assignment.

Up-titration or “pseudo-titration” will occur for all patients two weeks after start of trial medication and again after another two weeks, regardless of dose group (see [Table 4.1.4: 1](#)). Pseudo-titration is a term used to describe when patients are told that they are potentially assigned to a higher dose, but actually remain on the same dose:

- Patients in Dose Group 1 (1 mg TID) will be “pseudo-titrated” to 1 mg TID after two weeks and to 1 mg TID two weeks after that.
- Patients in Dose Group 2 (2 mg TID) will be up-titrated from 1 mg TID to 2 mg TID after two weeks and then “pseudo-titrated” to 2 mg TID two weeks after that.
- Patients in Dose Group 3 (3 mg TID) will be up-titrated from 1 mg TID to 2 mg TID after two weeks and to 3 mg TID two weeks after that.

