6.2.3 Treatment period

The treatment period in this trial is 20 weeks. All visit procedures should be completed as indicated in the [flow chart](#).

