The analyses for dose-finding will be performed using MCPMod whereby several possible dose response models (patterns) will be evaluated to identify the best-fitting model or subset of models (refer to [Figure 7.5: 1](#)). If PoC is established, the statistically significant (best fitting) model(s) from the candidate set are refitted to the data to generate new estimates for all model parameters from the data. The final model will be obtained via model averaging across the significant models based on Akaike Information Criterion (AIC). The target dose(s) can be estimated from that model by incorporating information on the minimum clinically relevant effect and accounting for safety. Doses within the dose range investigated (0 to 9 mg, total daily dose) will be considered.

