7.4 RANDOMISATION

BI will arrange for the randomisation and the packaging and labelling of trial medication. The randomisation list will be generated using a validated system, which involves a pseudo-random number generator so that the resulting treatment will be both reproducible and non-predictable. The block size will be documented in the Clinical Trial Report. Access to the codes will be controlled and documented.

In order to ensure a balance of patients who are on SGLT2 inhibitors and who are type 1 or 2 diabetes mellitus compared with those who are not, the trial will be stratified according to SGLT2 inhibitor use and type of diabetes mellitus at randomisation. Patients will be randomised to 1 mg tid, matching placebo, 2 mg tid, matching placebo, 3 mg tid, and matching placebo in a 3:1:3:1:3:1 ratio. There will be 60 patients on BI 685509 and 20 on placebo in each dose group (240 in total).

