7.8.1 Adverse Events

Analyses of AEs will be descriptive in nature. All analyses of AEs will be based on the number of patients with AEs and NOT on the number of AEs.

Furthermore, for analysis of AE attributes such as duration, severity, etc. multiple AE occurrence data on the CRF, will be collapsed into AE episodes provided that all of the following applies:

- The same MedDRA lowest level term was reported for the occurrences
- The occurrences were time-overlapping or time-adjacent (time-adjacency of 2 occurrences is given if the second occurrence started on the same day or on the day after the end of the first occurrence)
- Treatment did not change between the onset of the occurrences OR treatment changed between the onset of the occurrences, but no deterioration was observed for the later occurrence

For further details on summarisation of AE data, please refer to "Analysis and presentation of adverse event data from Clinical Trials" [\(9\)](#) and "Handling of missing and incomplete AE da [\(4\)](#).

The analysis of AEs will be based on the concept of TEAEs. That means that all AEs occurring between first drug intake until 7 days after last drug intake will be assigned to the randomised treatment. All AEs occurring before first drug intake will be assigned to 'screening' and all AEs occurring after last drug intake + 7 days will be assigned to 'follow-up' (for listings only). AEs that start before first drug intake and deteriorate under treatment will also be considered as 'treatment-emergent'. For details on the treatment definition, see [Section 6.1](#).

If only the start date of an AE is collected (without start time), any AE occurrence on the same day as the first BI 685509 administration will be assigned to the on-treatment phase. AEs will also be summarised by the treatment at the onset of AE for any drug-related AE. In addition, a summary of patients with down-titration due to AE will be provided.

An overall summary of AEs will be presented.

Frequencies [N (%)] of patients with AEs will be summarised by dose group, primary system organ class, preferred term (using MedDRA), and intensity. Separate tables will be provided for patients with serious AEs (SAEs), patients with AEs of Special Interest (AESIs), patients with fatal AEs, and patients with discontinuations due to AEs.

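### The supplementary AE summary by treatment at onset should cover all TEAEs and carry a defined dose, a denominator and patient-time, because planned time on dose differs

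*SAP*

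**What the plan says.** Dosing (protocol 3.1, 3.2 and 4.1.4): "All patients will start on 1 mg TID BI 685509 or matching placebo". If the drug is tolerated, dose groups 2 and 3 step to 2 mg TID after two weeks, and dose group 3 steps to 3 mg TID two weeks later. On duration, protocol 6.2.3 states: "The treatment period in this trial is 20 weeks".

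AE reporting (SAP 7.8.1, protocol 7.2.5) uses two attributions.

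- The main one assigns all treatment-emergent AEs (TEAEs), from first intake to 7 days after the last, to the randomised treatment. Separate tables cover serious AEs, AESIs, fatal AEs and discontinuations due to AEs.
- The additional one is: "AEs will also be summarised by the treatment at the onset of AE for any drug-related AE".

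The metric is given as: "All analyses of AEs will be based on the number of patients with AEs and NOT on the number of AEs". Hypotension and syncope AESIs also get an event-based summary. SAP section 7 has a general rule that percentages use all patients in the patient set, but no rule specific to the at-onset table. SAP 6.1 labels the on-treatment phase only as placebo or BI 685509, without dose, and assigns AEs during interruptions to the randomised treatment.

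On blinding, protocol 3.2 states: "Therefore investigators will know which dose group their patient is in". They remain blinded to active versus placebo. On dose choice, protocol 7.2.2 states: "The target dose(s) can be estimated from that model by incorporating information on the minimum clinically relevant effect and accounting for safety". SAP 7.4.1 likewise brings safety into the choice. Neither names a safety table.

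**The concern.** The at-onset summary is the planned AE table that links an event to the treatment being taken when it began. Two features make it hard to read.

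First, it counts patients without regard to time. The 1 mg column would collect short two-week exposures from dose groups 2 and 3 as well as 20-week exposures from dose group 1, while the 3 mg column would hold 16-week exposures only. A crude percentage then mixes risk with time on dose.

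Second, its case definition is a relatedness judgement made by someone who knows the dose group. Protocol 5.2.6.1.6 lists an indication of dose-response among the arguments for causality, so attribution could follow known dose. No all-TEAE table by actual dose is planned as a check.

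Safety is to inform the target dose. If this table were read for dose trend, it could suggest a gradient, or hide one, for reasons unrelated to the drug.

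**Working it through.** **Inputs.** Protocol 7.4 gives 3:1:3:1:3:1 allocation of 240 patients. 240 × 3/12 = 60 active and 240 × 1/12 = 20 placebo per dose group, so 60 / 60 / 60 active and 60 placebo in all. This reproduces the plan's figures. The schedule comes from protocol 4.1.4. The documents give no AE rate, so the hazard is an assumption. Full adherence and no dropout are also assumed.

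**Planned exposure by dose taken.**

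- 1 mg TID: 60 × 20 + 120 × 2 = 1440 patient-weeks in 180 patients, mean 8
- 2 mg TID: 60 × 18 + 60 × 2 = 1200 in 120 patients, mean 10
- 3 mg TID: 60 × 16 = 960 in 60 patients, mean 16
- Placebo: 60 × 20 = 1200 in 60 patients, mean 20

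**Null table.** Take the same constant hazard λ at every dose and on placebo. A patient counts at a dose if at least one event starts during time on it, with probability 1 − exp(−λ × weeks). At λ = 0.01 per week:

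- 1 mg: 60 × (1 − e^−0.20) + 120 × (1 − e^−0.02) = 10.88 + 2.38 = 13.25
- 2 mg: 60 × (1 − e^−0.18) + 60 × (1 − e^−0.02) = 9.88 + 1.19 = 11.07
- 3 mg: 60 × (1 − e^−0.16) = 8.87
- Placebo: 60 × (1 − e^−0.20) = 10.88

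| Denominator | 1 mg | 2 mg | 3 mg | Placebo |
|---|---|---|---|---|
| Ever on the dose (180/120/60/60) | 7.4% | 9.2% | 14.8% | 18.1% |
| Randomised (60 each) | 22.1% | 18.5% | 14.8% | 18.1% |

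The first row doubles from 1 to 3 mg (14.8/7.4 = 2.0). The second falls by a third (14.8/22.1 = 0.67). With ever-exposed denominators, λ = 0.005 gives 3.8 / 4.8 / 7.7% and λ = 0.02 gives 13.6 / 17.1 / 27.4%. Under the same null, the table by randomised arm shows 18.1% in all four arms.

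**Do person-time rates cure it?** At λ = 0.01, patients with an event per 100 planned patient-weeks are 13.25/1440 = 0.92, 11.07/1200 = 0.92, 8.87/960 = 0.92, and 10.88/1200 = 0.91 on placebo. The trend disappears when the hazard is constant.

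It does not disappear otherwise. Assume 20% incidence over 20 weeks in every arm, with risk in weeks 0–4 five times the later risk. The later hazard is −ln(0.8)/(16 + 4 × 5) = 0.0062 per week and the early one 0.031. The rates per 100 patient-weeks become 1.33 / 1.04 / 0.59 for 1 / 2 / 3 mg, a false fall. Rates by actual dose therefore need randomised-arm comparisons within common calendar windows beside them.

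**Limit of the windows.** Assume 3% per week for the first two weeks after reaching any dose and 0.5% otherwise, the same at every dose. From week 4 to 20, dose groups 1 and 2 each accumulate 16 × 0.005 = 0.08, and dose group 3 accumulates 2 × 0.03 + 14 × 0.005 = 0.13. Incidence is then 7.7%, 7.7% and 12.2%. The last window contains the step to 3 mg, which only dose group 3 has, and must be labelled so.

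**The case against.** The strongest reply is that the main safety analysis is unaffected. It covers all TEAEs, related or not, by randomised arm with equal planned duration, and it is flat under the null above. Counting 1 mg events under a higher group is no error there, because the table compares titrated regimens as randomised. This stands, and that table should remain primary.

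A reader might infer that the planned AE reporting as a whole will give dose selection a false trend. The documents do not support that. The at-onset summary is additional and descriptive, and no section makes it the basis for dose choice. A reader might also take the apparent doubling from 1 to 3 mg as the expected result. That needs the ever-exposed denominator, which the SAP does not state; its general percentage rule points elsewhere, and with 60 per column the trend reverses. Nor is up-titration forced: it depends on tolerance, and patients down-titrated or interrupted for a related AE may not go back up. That selection tends to make higher-dose events look fewer.

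Three further points carry some weight.

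- The sponsor's AE standard (SAP reference 9) is not available and may set a denominator or add rates.
- Inflated attribution in a known dose group would also touch that group's own placebo patients, which limits the bias if placebo is shown by dose group.
- Hypotension and syncope get event-based summaries, and AE-related down-titrations are summarised. Neither uses time at risk.

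What remains is a supplementary table whose dose definition and denominator are not stated and whose stated metric ignores unequal time.

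**Conclusion.** This is a worthwhile, inexpensive improvement to a supplementary table and does not undermine the main safety comparison. From the documents alone, planned mean time on dose is 8, 10 and 16 weeks at 1, 2 and 3 mg TID. The at-onset summary is limited to drug-related AEs judged by investigators who know the dose group, and the available SAP text plans no patient-time.

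The size of the artefact, a doubling or a one-third fall with no dose effect, rests on an assumed constant hazard of 1% per week, full adherence, treatment at onset read as actual dose, and one of two denominators. The direction cannot be settled from the SAP. An effect on dose selection would arise only if this table were used for it, which the documents leave open because they name no safety table.

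**What to change.** In SAP 7.8.1, with matching wording in protocol 7.2.5:

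1. Define treatment at onset as the dose actually taken, and extend the summary from drug-related AEs to all TEAEs and AESIs.
2. Show patients at risk and patient-weeks by actual dose, with rates per 100 patient-weeks.
3. Add all-TEAE incidence by randomised arm within common windows: weeks 0–2, weeks 2–4, and week 4 to EoT.
4. State that the randomised-arm tables, overall and windowed, are the safety input to dose selection, and that the at-onset table is descriptive.

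The cost is SAP wording and a few tables. Under SAP 7.7 the date and time of each drug administration are already listed. Footnotes should say that rates by actual dose assume a constant hazard, that tolerability selection and carry-over after a dose step affect them, and that the week 4 to EoT window includes the step to 3 mg in dose group 3 only.

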3.3.2 Inclusion criteria

1. Signed and dated written informed consent in accordance with ICH-GCP and local legislation prior to admission to the trial.
2. Male or female patients aged ≥ 18 years at time of consent.
3. eGFR (Chronic Kidney Disease Epidemiology Collaboration [CKD-EPI] formula) ≥ 20 and < 90 mL/min/1.73 m² at Visit 1 by central laboratory analysis. eGFR must remain \geq

- 20 mL/min/1.73 m² after Visit 1 up to the start of Visit 3, measured by central or any local laboratory analysis.
4. UACR ≥ 200 and $< 3,500$ mg/g in spot urine (midstream urine sample) by central laboratory analysis at Visit 1.¹
 5. Treatment with the highest tolerated dose of either ACEi or ARB (but not both together), and stable dose for ≥ 4 weeks before Visit 1 with no planned change of the therapy during the trial.
 6. If the patient is taking any of the following medications they should be on a stable dose at least 4 weeks prior to visit 1 until start of treatment, with no planned change of the therapy during the trial: anti-hypertensives, NSAIDs, endothelin receptor antagonists, systemic steroids or SGLT2 inhibitors.
 7. Patients with stable type 1 or type 2 diabetes mellitus, diagnosed before informed consent. Treatment (including SGLT2 inhibitor and/or GLP1 receptor agonist) should have been unchanged or changes deemed minor (according to investigator's judgement) within 4 weeks before Visit 1 and until start of trial treatment.
 8. Glycated Haemoglobin (HbA1c) $< 10.0\%$ at Visit 1 measured by the central laboratory.
 9. Seated SBP ≥ 110 and ≤ 160 mmHg and DBP ≥ 65 and ≤ 110 mmHg at Visit 1 and optimized anti-hypertensive treatment according to local standard of care and investigator's judgement.²
 10. Body Mass Index (BMI) ≥ 18.5 and < 50 kg/m² at Visit 1.
 11. Male patients able to father a child must be willing to use condoms if their sexual partner is a Women of child-bearing potential³ (WOCBP). WOCBP must be ready and able to use highly effective methods of birth control per ICH M3 (R2). Such methods should be used throughout the trial. A list of contraceptive methods meeting these criteria is provided in the patient information and in [section 4.2.2.3](#) of the protocol.

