7.8 SAFETY ANALYSIS

All safety analyses will be performed on the TS following BI standards. No hypothesis testing is planned. All safety analyses will be performed on treatment set.

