Regarding AESIs, summaries of AESIs of hypotension and syncope will be presented for both patient-based and event-based analyses. An individual episode of hypotension will be considered as significant or non-significant based on baseline BP and the lowest BP during the episode. Criteria for significant hypotensive episode are:

- For patients with baseline SBP ≤ 140 : decrease $((\text{lowest SBP during the episode} - \text{baseline SBP}) / (\text{baseline SBP})) \geq 30\%$
- For patients with baseline SBP > 140 : decrease $((\text{lowest SBP during the episode} - \text{baseline SBP}) / (\text{baseline SBP})) \geq 40\%$
- Or, lowest SBP during the episode < 90
- For patients with baseline DBP ≤ 70 : $((\text{lowest DBP during the episode} - \text{baseline DBP}) / (\text{baseline DBP})) \geq 30\%$
- For patients with baseline DBP > 70 : $((\text{lowest DBP during the episode} - \text{baseline DBP}) / (\text{baseline SBP})) \geq 40\%$
- Or, lowest DBP during the episode < 50
- Lowest mean arterial pressure (MAP) during the episode < 70

Details of the AESI of Hypotension and Syncope will be also listed.

Category	Safety topic	Definition
AESI	Hypotension	Investigator-reported, as a dedicated AE category on the AE eCRF page
AESI	Syncope	Investigator-reported, as a dedicated AE category on the AE eCRF page

In addition, potential DILI, acute kidney injury, and QT-interval prolongation are defined as follows:

- Potential DILI, defined as: Narrow sub-SMQ ‘Liver related investigations, signs and symptoms’, narrow sub-SMQ ‘Cholestasis and jaundice of hepatic origin’, narrow sub-SMQ ‘Hepatitis, non-infectious’ and narrow sub-SMQ ‘Hepatic failure, fibrosis and cirrhosis and other liver damage-related conditions’, or investigator-reported AESIs.
- Acute kidney injury, defined as: SMQ ‘Acute renal failure’, narrow scope
- QT-interval prolongation, defined as: SMQ ‘Torsade de points/QT prolongation’, narrow scope excluding the PT ‘Syncope’.

Summaries of potential DILI, acute kidney injury, and QT-interval prolongation will be presented for patient-based analyses.

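### SAP 7.8.1: the hypotension criterion for baseline DBP above 70 divides a diastolic change by baseline SBP, so some diastolic falls of 40% or more are labelled non-significant

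*SAP*

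**What the plan says.** SAP section 7.8.1 sets a classification rule for the AESI of hypotension: "An individual episode of hypotension will be considered as significant or non-significant based on baseline BP and the lowest BP during the episode". The criteria that follow come in a systolic group, a diastolic group and a limit on mean arterial pressure (MAP).

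- **Systolic percentage criteria.** The threshold is 30% for baseline SBP up to 140 and 40% above it. Both divide by baseline SBP; the second reads "For patients with baseline SBP > 140 : decrease $((\text{lowest SBP during the episode} - \text{baseline SBP}) / (\text{baseline SBP})) \geq 40" (per cent).
- **Diastolic, baseline DBP up to 70.** "For patients with baseline DBP ≤ 70 : $((\text{lowest DBP during the episode} - \text{baseline DBP}) / (\text{baseline DBP})) \geq 30" (per cent). This divides by baseline DBP.
- **Diastolic, baseline DBP above 70.** "For patients with baseline DBP > 70 : $((\text{lowest DBP during the episode} - \text{baseline DBP}) / (\text{baseline SBP})) \geq 40" (per cent). This divides by baseline SBP.
- **Absolute limits.** Lowest SBP below 90; "Or, lowest DBP during the episode < 50"; lowest MAP below 70.

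Two statements limit the consequences. On individual cases, section 7.8.1 says "Details of the AESI of Hypotension and Syncope will be also listed". On safety analysis in general, section 7.8 says "No hypothesis testing is planned".

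**The concern.** The two diastolic criteria repeat the structure of the two systolic ones: 30% below a cut-point, 40% above it, each relative to baseline. Only the criterion for baseline DBP above 70 changes to the other pressure. Neither the SAP nor the protocol defines or justifies a mixed ratio, so it looks like SBP written for DBP.

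Because SBP exceeds DBP, the printed ratio is always smaller than the true percentage fall in DBP. The error therefore runs one way: it can only move episodes from significant to non-significant. Hypotension is a named risk of the drug in Protocol section 1.4.2 and an AESI in section 5.2.6.1.4, so the label should mean what it appears to mean. A programmer must otherwise either code the formula as printed or depart from it without authority.

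**Working it through.** The plan gives no figure to reproduce here; the check works through the definition itself.

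**Inputs.** The criteria come from SAP 7.8.1. The illustrative baseline range comes from Protocol 3.3.2, criterion 9: "Seated SBP ≥ 110 and ≤ 160 mmHg and DBP ≥ 65 and ≤ 110 mmHg at Visit 1".

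**Assumptions.**
- Each percentage is read as a decrease. All four expressions are lowest minus baseline, which is negative for a fall, and only the systolic ones say that a decrease is meant.
- The criteria are joined by 'or'.
- MAP = DBP + (SBP − DBP)/3, so MAP is below 70 when SBP + 2 × DBP is below 210.

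**Step 1: fall required.** As printed, the diastolic fall must be at least 0.4 × baseline SBP. With the DBP denominator it must be at least 0.4 × baseline DBP.

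| Baseline | Fall needed, printed | As share of DBP | Fall needed, DBP denominator |
|---|---|---|---|
| 140/80 | 56 | 70.0% | 32 |
| 150/90 | 60 | 66.7% | 36 |
| 160/100 | 64 | 64.0% | 40 |

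**Step 2: when the criterion adds anything to lowest DBP below 50.**
- As printed, only when baseline DBP − 0.4 × SBP is at least 50, that is, from baseline DBP 94 at SBP 110, 106 at SBP 140 and 114 at SBP 160. The last is above the entry maximum of 110.
- With the DBP denominator, when 0.6 × baseline DBP is at least 50: 50/0.6 = 83.3, or 84 in whole mmHg.
- For baseline DBP of 71 to 83 the choice of denominator makes no difference.
- The criterion for baseline DBP up to 70 is redundant in any case: 0.7 × 70 = 49, already below 50.

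**Step 3: episodes whose label changes at baseline SBP 140.** All other criteria must fail. Lowest SBP must be at least 99 (a 30% fall gives 98), and SBP + 2 × DBP must be at least 210.

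| Baseline | Lowest DBP | Lowest SBP |
|---|---|---|
| 140/83 | none | none |
| 140/84 | 50 | at least 110 |
| 140/90 | 50 to 54 | at least 110 (DBP 50), falling to 102 (DBP 54) |
| 140/100 | 50 to 60 | at least 110, falling to 99 |
| 140/110 | 55 to 66 | at least 100 (DBP 55), 99 (DBP 56 to 66) |

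**Step 4: worked episodes.**
- 140/90 to 110/54: 36/90 = 40.0%, scored 36/140 = 25.7%. SBP falls 30/140 = 21.4% and MAP is 218/3 = 72.7. Nothing else catches it.
- 150/100 to 115/60: 40/100 = 40.0%, scored 40/150 = 26.7%. SBP falls 35/150 = 23.3% (threshold 40%) and MAP is 235/3 = 78.3. Nothing else catches it.
- Counter-example, 140/90 to 101/54: MAP is 209/3 = 69.7, so the MAP limit catches it and the label does not change.

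**Step 5: extent over the entry range.** Take whole-mmHg baselines with SBP 110 to 160, DBP 71 to 110 and pulse pressure of at least 20, which gives 1,830 pairs. The criterion can be the only one met in 154 pairs as printed and in 1,167 with the DBP denominator. These are pairs where it is possible, not patients: at 110/84, for example, it would need SBP not to fall at all.

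**The case against.** The wording and arithmetic are not in dispute; the case against concerns weight.

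- **Few episodes can qualify.** Protocol 5.2.6.1.4 makes the AESI severe hypotension in the investigator's judgement, and 5.2.6.1.5 defines severe as incapacitating. To change label, such an episode must have baseline DBP of at least 84, lowest DBP of at least 50, SBP of at least 90 and MAP of at least 70. Nothing in the documents shows that this is likely. This stands, and it is why the point is minor.
- **No named output depends on the label.** The SAP ties no specific table or decision to the significant/non-significant split, and affected episodes stay visible in the listing. This also stands. It limits the harm but does not make the definition right.
- **The rule for combining criteria is unstated.** If the systolic, diastolic and MAP groups were joined by 'and', none of the episodes listed above would change label, and a different set would be affected. 'Or' is the more natural reading, but the SAP should say so.
- **The cause may be a misread letter, or intended.** The text was extracted from PDF and the discrepancy is one letter. Nothing at that place suggests a misreading, but a look at the source file settles it. The sponsor's intent is not documented, so it should be confirmed.

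**Conclusion.** The concern holds. As written, the criterion for baseline DBP above 70 is inconsistent with the other three and stricter than a 40% diastolic fall. For baseline DBP of 84 or more, some falls of 40% or more are labelled non-significant with no other criterion to catch them.

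The effect stops at a descriptive sub-label of investigator-reported episodes. AESI counts, individual listings and efficacy results do not change, and no hypothesis test depends on it. Severity is minor.

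The size rests on the assumptions listed with the calculation. In addition, the Visit 1 entry range stands in for the analysis baseline, which SAP 6.7 takes from the last value before first dose. How often the label would change cannot be stated, because the documents give no blood pressure distribution.

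**What to change.** In SAP 7.8.1, confirm the intended denominator for the criterion at baseline DBP above 70 and change it to baseline DBP; if the mixed ratio was meant, say so and give the reason. Write all four percentage criteria as (baseline − lowest)/baseline of the same pressure, which also settles the sign. Leave every threshold unchanged. In the same edit, state whether the criteria combine by 'or' and which MAP formula applies, since the classification depends on both.

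The cost is one word plus short clarifying text in the SAP, and one line of code, before unblinding. No new data are needed and no other analysis is affected.
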